**Specific Aim 2) To assess the effects of the aerobic activity on interhemispheric inhibition using fMRI and TMS.**

*Introduction.* The PI's previous research line has indicated that increased aerobic activity level is associated with decreases in aging-related loss of interhemispheric inhibition ([name] et al., 2009; [name] et al., 2011). In a previous project, we have noted that in fMRI, highly-fit elderly and middle age adults show lower bilateral positive BOLD activity in the primary motor cortex. Further, highly fit individuals show patterns of activity more similar to younger adults in that they show a negative BOLD signal in the ipsilateral primary motor area likely indicating an active suppression. In TMS, highly fit elderly and middle age adults show a longer duration of the ipsilateral silent period, a putative measure of transcallosal inhibition (Meyer et al., 1995).

We will test the hypothesis that an aerobic activity intervention can mitigate or reverse aging-related loss of interhemispheric inhibition as measured by fMRI and TMS. We will also test the hypothesis that behavioral training of unimanual activity acts to alter interhemispheric communication dynamics and this is a potential mechanism of improvement in motor performance.

*Research Design and measures.* fMRI and TMS paradigms are discussed below.

*fMRI tasks.* Two block-design right-hand motor tasks will be used to evaluate interhemispheric cortical activation patterns. Both tasks have been reported sensitive to aging-related differences in interhemispheric inhibition ([name] et al., 2009; Ward et al., 2008). Blocks will consist of seven images (28 seconds) for both rest and active conditions and six block cycles (alternating between 7 rest images and 7 active images) will comprise each run (5 minutes 36 seconds). In the scanner, participants will engage in two runs of each motor task and all performance data (accuracy, reaction times) will be saved for later analysis. Participants will train on the both tasks outside of the scanner and again inside the scanner immediately prior to data acquisition. Mirror movements (symmetric movement of the opposite hand) are of concern for unimanual digit manipulations. To monitor for such movements, force output of the left first dorsal interosseous muscle (FDI) will be recorded during practice sessions.

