*Functional Imaging and Neurophysiological Analyses.* Functional images will be analyzed and overlaid onto structural images with the Analysis of Functional Neuroimaging (AFNI) program (Cox, 1996). To minimize the effects of head motion, time series images will be spatially registered in 3-dimensional space. The average functional intensity of each acquired slice for every subject will be normalized to the mean intensity of all slices for all subjects to control for differences in functional intensity between subjects. A subject's data will be excluded from further analyses if any time series of a subject is judged from visual inspection to contain a significant number of images with gross artifacts or residual motion.

*fMRI Analysis.* The current study is concerned with the response of the ipsilateral primary motor cortex during actions performed by right hand. It is hypothesized that sedentary aged adults will initially show an increase in metabolic activity (i.e. – a positive BOLD response) in this area. To assess this, an analysis of average hemodynamic (impulse) response functions in the right primary motor cortex will be performed. These impulse response profiles will be tested across session using repeated measures ANOVA. Significant differences will be assessed at the individual

subject and group level.

For group analysis of intervention effects, anatomic and functional images will be interpolated to volumes with 1 mm^3 voxels, co-registered, and converted to stereotaxic space of Talairach and Tournoux (1988) using AFNI. Estimates of hemodynamic response functions (HRFs) generated from a deconvolution procedure will be spatially smoothed using a 5 mm full-width half-maximum (FWHM) Gaussian filter to compensate for variability in structural and functional anatomy across participants. Area under the curve (AUC) of the HRF's will be entered into a voxel-wise two-way mixed-design ANOVA (age grouping as the between subjects factor, session as the within-subjects factor). Additional pair-wise comparisons of age groupings will be performed using Student's t-test ( $p < .05$ , False Discovery Rate corrected) on a voxel-by-voxel basis with left and right primary motor cortices selected as regions of interest (ROI). Pairwise comparisons will be computed for all motor response conditions.

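### fMRI response size is scaled by slice averages to a study-wide mean, with no percent-of-baseline step stated; this adds avoidable scale noise and leaves open a conditional downward bias in right M1

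*Combined protocol and SAP*

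**What the plan says.** All of this stands in section 5, Specific Aim 2, of the combined protocol and SAP.

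- **Registration.** To limit head motion, "time series images will be spatially registered in 3-dimensional space".
- **Intensity scaling.** "The average functional intensity of each acquired slice for every subject will be normalized to the mean intensity of all slices for all subjects". The stated purpose is "to control for differences in functional intensity between subjects".
- **Response estimate.** "Estimates of hemodynamic response functions (HRFs) generated from a deconvolution procedure will be spatially smoothed".
- **Group analysis.** "Area under the curve (AUC) of the HRF's will be entered into a voxel-wise two-way mixed-design ANOVA", with session as the within-subject factor. Pairwise voxel-level tests follow in the left and right motor-cortex regions of interest.
- **Target.** "an analysis of average hemodynamic (impulse) response functions in the right primary motor cortex will be performed", and the profiles are tested across sessions by repeated-measures ANOVA.
- **Meaning of the sign.** Of highly fit people, the Aim 2 introduction says "they show a negative BOLD signal in the ipsilateral primary motor area likely indicating an active suppression".

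The research design for Aim 1 lists change in fMRI measures among the primary outcomes. The plan has five assessments: enrolment, after the waiting period, after each of the two interventions, and at the end of the final six months.

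The documents do not state percent signal change or division by a voxel's own baseline. Nor do they say whether the slice average is taken once per run or for each image, whether it covers brain voxels only, or in which plane slices are acquired.

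**The concern.** The area under a response curve is an amplitude, so it carries whatever factor the data were multiplied by. A slice average corrects for gain that affects the whole slice. It does not put voxels on a common scale, because it also depends on what else is in the slice: how much is brain, how the head is tilted, where the slice falls. A person rescanned with slightly different placement can show a changed amplitude without any change in physiology.

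A second possibility is more specific to this trial. If the scaling is done image by image, the slice average is held flat over time. Activation in one part of the slice must then be offset by an apparent fall elsewhere in it. With right-hand movement the activation is mainly in left M1, and the apparent fall could include right M1, where the plan reads a negative response as suppression. The bias would vary with left-M1 activation, which training may itself change.

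**Working it through.** The plan gives no figure for the effect of its scaling, so there is none to reproduce. Its block timing is consistent: 28 s / 7 images = 4 s per image; six cycles of 14 images = 84 images; 84 x 4 s = 336 s = 5 min 36 s, as stated. I used that 84-image rest/active design and fitted an intercept and a boxcar by least squares. All intensities, activation sizes and CVs below are assumptions, because the documents give none.

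**Case 1: one constant factor per slice.**

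Factor k = grand mean / slice mean. Amplitude = k x voxel baseline x true percent response. Assume grand mean 1000, voxel baseline 900 and a true response of 1%:

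| Slice mean | Amplitude | Percent of own baseline |
|---|---|---|
| 600 | 1000/600 x 9 = 15.0 | 1.00% |
| 800 | 1000/800 x 9 = 11.25 | 1.00% |
| 1000 | 9.0 | 1.00% |
| 1200 | 1000/1200 x 9 = 7.5 | 1.00% |

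Across this assumed range the amplitude differs two-fold for the same response. The last column divides by the fitted rest level. Dividing by the run mean gives 0.01/1.005 = 0.995% in every row, again independent of slice mean. Because k is positive and constant within a run, the sign and the within-run t-statistic do not change.

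The noise in a change score, for a session-to-session scale CV and R = mean response / SD of change, is approximately:

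variance inflation = 1 + 2 x CV^2 x R^2

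| R | CV 10% | CV 20% | Equivalent loss out of 40, as 40 x (1 - 1/inflation) |
|---|---|---|---|
| 1 | 1.02 | 1.08 | 0.8 to 3.0 |
| 3 | 1.18 | 1.72 | 6.1 to 16.7 |

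The lower row needs a mean response three times the SD of change. That is plausible, if anywhere, in left M1, where responses are large. It does not describe an ipsilateral response near zero.

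**Case 2: each image scaled by its own slice mean, with both motor cortices in that slice.**

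Let f be the share of slice signal that activates and a the size of that activation. A right-M1 voxel with no true response then reads 1/(1 + f x a) - 1, which is about -f x a:

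| f | a = 1% | a = 2% | a = 3% |
|---|---|---|---|
| 1% | -0.01% | -0.02% | -0.03% |
| 2% | -0.02% | -0.04% | -0.06% |
| 5% | -0.05% | -0.10% | -0.15% |
| 10% | -0.10% | -0.20% | -0.30% |

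A simulated noisy slice of 1000 voxels, 50 of them active at 2%, gave -0.096% in the inactive voxels under per-image scaling and +0.006% under run-mean scaling.

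A true right-M1 response of +0.2% reads (1.002)/(1 + f x a) - 1:

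- f = 2%, a = 2%: +0.16%
- f = 5%, a = 2%: +0.10%
- f = 5%, a = 3%: +0.05%
- f = 10%, a = 3%: -0.10%

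Only the last, extreme combination reverses the sign. If slices are sagittal, left M1 is not in the right-M1 slice, its contribution to f is 0, and there is no left-to-right artefact.

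**Does a later division by baseline repair it?** In case 1 yes: k cancels. In case 2 no: the time course is already distorted, and the false fall remains.

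**The case against.** The strongest reply is that the sentence describes scaling between people. Its stated purpose is "to control for differences in functional intensity between subjects", and it speaks of slices, whereas elsewhere the protocol calls time points images. On that reading the factor is constant over a run. It cannot change the sign of the right-M1 response, and it leaves untouched any measure thresholded within a run, such as the share of ipsilateral motor cortex recruited, which section 7 uses for Aim 3. The TMS measures are unaffected in any case. All of this stands, and it makes case 1 the more natural reading.

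It is also fair to say that silence on percent scaling is not a decision against it. The units of the area are unstated, and a later conversion is possible. A reader should therefore not infer that the sponsor rejected baseline scaling.

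A reader might go further and infer that the plan manufactures a false negative right-M1 response. The documents do not support that. It needs per-image scaling, which is not stated, and both motor cortices in one acquired slice, which cannot be checked because the plane is not given. A reader might also take 6 to 17 lost participants out of 40 as the cost. That figure applies only at R = 3 with assumed CVs and does not describe the right-M1 target.

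What remains is that the one scaling rule the plan does state leaves amplitude dependent on slice content, and so meets its own purpose only in part. The wording does not exclude the per-image version.

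**Conclusion.** The point holds in a limited form. As written, the area under the response depends on slice content and placement as well as on the percent response.

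Under a constant slice factor the consequence is extra noise, not a false sign. Change-score variance rises about 2-8% at R = 1 for assumed scale CVs of 10-20%, and more only where responses are large.

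Under per-image scaling with both motor cortices in the same slice, right M1 is biased downward by about f x a, for example -0.1% at an assumed 5% active and 2% activation. That would usually shrink a clear positive response without reversing it. It still matters, because the shift is in the direction the trial interprets as inhibition and follows left-M1 activation.

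Neither the session-to-session CV, the active share nor the activation size comes from the documents, so these sizes are illustrations over a range. The case for change does not depend on their exact values, since the alternative is standard, nearly free and removes both problems.

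**What to change.** Replace the slice normalisation with percent signal change. After registration, divide each in-brain voxel's time series in each run by that voxel's own run mean and multiply by 100. Then run the deconvolution and compute the area under the response in those units for every session. State that no slice or global scaling of individual images is applied, and give the acquisition plane.

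The new step must take the place of the slice step, not follow it, because division after per-image scaling leaves the false fall in right M1.

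The cost is one standard processing step in exchange for another, with no new data. The small downside is that a brain mask or low-signal threshold must be specified, so that voxels with near-zero baseline are not used as divisors.

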*Research Design.* The proposed study will examine 40 older, sedentary Veterans from the greater Atlanta area. Participants will be randomly assigned to one of two 15-month intervention conditions involving aerobic fitness training and behavioral training. The study is a reversal design in which both groups are assessed pre-treatment with both fMRI and TMS measures, as well as behavioral measures at study enrollment. As part of the design, both groups will undergo a 3-month waiting period during which they will engage in an organized stretching routine with no aerobic exercise component. After this waiting period, the participants again undergo behavioral, fMRI and TMS assessments. At this point, the participants will be assigned to either a behavioral treatment group involving a motor coordination protocol previously shown to improve upper extremity motor performance in older adults (Christou et al, 2011) or a supervised aerobic training group at the Atlanta VA Medical Center. The design of the study is depicted in the in Figure 6 below. The primary outcomes of this aim are changes in fMRI and TMS measures of interhemispheric communication and motor performance tests.

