## 7. Statistical Analysis

**Statistical Analysis for Specific Aim 1.** We will model each of the outcome measures in Aim 1 (upper extremity) jointly using a mixed linear model to determine whether the mean responses of the groups are significantly different across the time points. We expect that modeling the outcomes jointly, using subject as a random factor, will allow for some gains in power. Our fixed factors will be time, treatment group and their interaction. This model will enable us to estimate the overall effects of time and treatment, and most importantly, how the effects of treatment differ with time.

**Statistical Analysis for Specific Aim 2.** For each of the outcome measures in Aim 2 (changes in fMRI and TMS activity during unimanual tasks) we will use a mixed linear model to determine whether the mean responses of the groups are significantly different across the time points. Our fixed factors will be time, treatment group and their interaction. This model will enable us to estimate the overall effects of time and treatment, and most importantly, how the effects of treatment differ with time.

**Statistical Analysis for Specific Aim 3.** For each of the outcome measures in Aim 3 we will use a mixed linear model to determine whether the mean responses of the groups are significantly different across the time points. Our fixed factors will be time, treatment group and their interaction. This model will enable us to estimate the overall effects of time and treatment, and most importantly, how the effects of treatment differ with time. Level of interhemispheric inhibition will be characterized by proportion of ipsilateral motor cortex recruited during fMRI tasks, ipsilateral silent period in TMS, and level of diminution of MEP size in the interhemispheric inhibition protocol in paired-pulse TMS.

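### Read literally, one scan run judged bad by eye discards all of a participant's fMRI data, including good sessions that the planned mixed model could use

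*Combined protocol and SAP*

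**What the plan says.** The rule is in Functional Imaging and Neurophysiological Analyses, under Specific Aim 2: "data will be excluded from further analyses if any time series of a subject is judged from visual inspection to contain a significant number". The count is of images spoiled by artifact or by movement left after registration. The unit removed is the subject, the trigger is any one time series, and the method is visual judgement. No number defines how many bad images are too many. The text names no alternative at run or session level, and does not say whether the rater knows the participant's group or the session.

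The number of time series follows from the design. Under fMRI tasks, "Two block-design right-hand motor tasks will be used to evaluate interhemispheric cortical activation patterns", and "participants will engage in two runs of each motor task". The Research Design under Specific Aim 1 says that "both groups are assessed pre-treatment with both fMRI and TMS measures" at enrollment, and then: "After this waiting period, the participants again undergo behavioral, fMRI and TMS assessments". Further imaging follows each of the two interventions and the six-month phase described under Specific Aim 3. That makes five scan sessions.

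For the Aim 2 outcomes, Section 7 plans a mixed linear model: "Our fixed factors will be time, treatment group and their interaction". Aim 3, whose measures include imaging, has the same model. The fMRI Analysis paragraph under Specific Aim 2 instead names repeated measures ANOVA across sessions and a voxel-wise mixed-design ANOVA.

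**The concern.** The fMRI measures are among the primary outcomes named in the Research Design under Specific Aim 1, and the sample size section is framed on the fMRI and TMS measures. A mixed model can use whichever sessions a participant has. A rule that deletes the participant before modelling removes that advantage: a bad run at the six-month scan would discard four earlier sessions that may be sound. Older adults who complete 15 months of training and testing could then contribute nothing to the imaging aims.

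There is also a question of selection. Participants are randomized after the waiting period, so three of the five sessions (12 of 20 runs) come after randomization. A judgement made by eye, without a stated threshold or stated masking, could depend on group or session.

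**Working it through.** **The plan's own figure.** Power Analysis and Sample Size gives a detectable effect of 0.83 with 20 per group, from a two-sample t-test on change, without stating power or sidedness. It therefore cannot be reproduced exactly. With alpha 0.05 (the level stated for the TMS tests, borrowed here) and the noncentral t distribution, 20 per group has 72.5% power at 0.83 two-sided, or 82.4% one-sided. The two-sided 72.5% is the baseline below. Planned enrollment of 24 per group allows for drop-out only; nothing is added for completers whose scans are excluded.

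**Runs per completer.** 2 tasks x 2 runs = 4 per session; 4 x 5 sessions = 20.

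**Loss under the literal rule.** Let p be the chance that one run fails inspection. The documents give no p, so 1%, 2% and 5% are assumptions.

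- Independent failures: share of participants lost = 1 - (1 - p)^20.
- Failures clustered within people: beta-binomial with assumed within-person correlation r = 0.3. With s = (1 - r)/r = 2.333 and b = (1 - p)s, share lost = 1 - product over i = 0 to 19 of (b + i)/(s + i).

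Power is the two-sided t-test power at 0.83, treating the expected number retained of 20 per group as fixed.

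| p | Lost, independent | Kept of 20 | Power | Lost, clustered | Kept of 20 | Power |
|---|---|---|---|---|---|---|
| 0 | 0% | 20 | 72.5% | 0% | 20 | 72.5% |
| 1% | 18.2% | 16.4 | 63% | 5.6% | 18.9 | 70% |
| 2% | 33.2% | 13.4 | 54% | 10.9% | 17.8 | 67% |
| 5% | 64.2% | 7.2 | 31% | 25.3% | 14.9 | 59% |

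For 40 completers at p = 5%, about 14 remain with independent failures (40 x 0.95^20 = 14.3) and about 30 with clustering (40 x 0.747 = 29.9).

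**Loss if the rule was meant per session.** With four runs and independent failures, 1 - (1 - p)^4 gives 3.9%, 7.8% and 18.5% of sessions lost at 1%, 2% and 5%.

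**What keeping the good sessions recovers.** A simulation of 1,500 trials per rate used 20 per group, five sessions, an assumed correlation of 0.5 between sessions, an effect of 0.83 SD of change and independent failures. It compared dropping only the affected session, with a mixed model on what remains, against deleting the whole subject. Power for the first-intervention contrast was 0.69 against 0.62 at 1%, 0.69 against 0.53 at 2%, and 0.59 against 0.26 at 5%. Simulation error is about 0.01.

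**Whether the two runs of a task are replicates.** Under Finger opposition motor task, both runs repeat the same paced task. Under Force matching task, one run is at 25% and the other at 35% of maximum voluntary contraction. The same paragraph gives muscle recruitment as a possible influence on ipsilateral inhibition. Dropping one force-matching run therefore loses a condition, not a repeat.

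**The case against.** **The rule may suit the analysis beside it.** The fMRI Analysis paragraph names repeated measures and mixed-design ANOVA, which usually need complete data. Whole-subject exclusion fits those methods. This stands as an explanation, but it also shows that the plan names two different analyses for the same outcomes.

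**The trigger is strict.** It asks for a substantial number of grossly affected images, or motion left after registration. Run failure could be rare, and it plausibly clusters in people who move a lot. This stands: at 1% with clustering, the loss is about 6% of participants and two to three points of power.

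**A per-session exclusion may have been meant.** The wording does not say so. If it was, the loss is smaller, and the undefined threshold and unstated masking remain.

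A reader might also infer several stronger things that the documents do not support:

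- That the plan's missing-data method is defeated. The plan states no such method; what is lost is the mixed model's ordinary ability to use incomplete participants.
- That the rater is unmasked. The documents are silent.
- That training changes movement in the scanner and so biases the comparison. Nothing in the documents shows this. By the fourth assessment both sequences have had both trainings, which makes differential exclusion by sequence less likely up to that point. The later split into exercise and no exercise has no such balance.
- That TMS and motor data are excluded too. The phrase about further analyses is not limited in words, but its place in the imaging section makes fMRI the natural reading.

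**Conclusion.** The point holds as a defect in a stated rule. Followed as written, it discards usable data on a primary outcome. The direction of the loss is certain, but its size is not, because it rests on assumed run failure rates and an assumed degree of clustering. Across 1% to 5%, between about 6% and 64% of participants lose all fMRI data, and two-sided power at 0.83 ends between 70% and 31%. The upper figures need independent failures at 5% and should not be quoted as the expected result. Selection related to treatment is possible, not shown. The plan should be changed, since the change is cheap and the rule acts on data that participants have already given.

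**What to change.** Replace subject-level exclusion with exclusion of only the affected data:

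- Set a numeric motion or artifact limit in advance, taken from the registration output, and apply it without knowledge of group or session.
- For finger opposition, drop the failed run and keep the other.
- For force matching, treat a failed run as a missing condition and include force level in the model. Do not let the surviving run stand for the session.
- Keep all remaining sessions in the Section 7 mixed model. Name that model as the fMRI intervention analysis, so that Section 7 and the ANOVA text under Specific Aim 2 agree.
- Report runs and sessions excluded, by group and session.

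The cost is a few sentences in the plan and one added model term, since image registration is already planned. The downside is small: some session values will be less precise or lack one force level.

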*TMS Analysis.* Six measures will be computed and analyzed from TMS acquisitions: Right FDI MEP size, right FDI MEP latency, recruitment curves (RC), ipsilateral silent period (iSP), interhemispheric inhibition at 10ms (IHI10) and 40ms (IHI40). The size of left FDI MEP evoked by TMS will be measured from peak-to-peak between TMS stimulation (first peak) and subsequent muscle response (second peak). The latency of MEPs will be measured from the onset of the stimulus presentation to the onset of the MEP. Recruitment curves will be evaluated based on slope generated from linear regression. Onset and end latency of the iSP will be taken at the initial and final intersections of the averaged signal with baseline indicating 80% of the background EMG level; the duration of EMG suppression between these two points will be computed. For each of the stimulation intensities, IHI will be expressed by  $(1 - \text{mean conditioned MEP} / \text{mean unconditioned MEP}) \times 100\%$ . Accordingly, IHI = 0%, IHI = 100%, and IHI < 0% will indicate no inhibition, complete inhibition, and interhemispheric facilitation, respectively. For within subjects comparison, repeated measures ANOVA with subsequent repeated measures pairwise t-tests will be generated. Group comparisons of TMS measures will be analyzed by between-subjects ANOVA and subsequent t-test pairwise comparisons. For all test, p-values < 0.05, corrected for multiple comparisons where applicable, will be considered statistically significant.

*BDNF Evaluation.* Fasting whole blood will be collected, by a certified phlebotomist, via venipuncture or peripheral venous line into pre-cooled plasma EDTA tubes and serum separator tubes (~40 ml per visit). Following collection, tubes will be transferred in sealed biohazard bags and in according with blood borne pathogens training standards to the Molecular Biology Lab (4A 178/4A 167) of the Atlanta VAMC Center of Excellence.

Plasma volume will be measured using methods described by Dill and Costill. Lactate will be measured by the Accusport Lactate Analyzer (Roche Molecular Biochemicals, Mannheim, Germany). Serum samples will be allowed to clot for 30 minutes before centrifugation at 1000g for 15 minutes. Plasma samples will undergo centrifugation within 30 minutes of collection at 1000g for 15 minutes at 2-8°C. Plasma aliquots will be separated and will then undergo an additional centrifugation "Super-

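### The fMRI plan assesses across-session change for significance within each participant, where scan-day variation cannot be separated from a training effect

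*Combined protocol and SAP*

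**What the plan says.** Under Specific Aim 2, fMRI Analysis, the average response in right M1 is compared between sessions: "These impulse response profiles will be tested across session using repeated measures ANOVA. Significant differences will be assessed at the individual" subject level and at group level. No error term, replicate unit or significance level is given for the individual-level test. The nearest statements cover other analyses. The TMS Analysis paragraph has "For all test, p-values < 0.05, corrected for multiple comparisons where applicable, will be considered statistically significant". The fMRI pairwise comparisons of groupings are "False Discovery Rate corrected) on a voxel-by-voxel basis with left and right primary motor cortices selected as regions of interest".

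The hypothesis for this aim is that "an aerobic activity intervention can mitigate or reverse aging-related loss of interhemispheric inhibition as measured by fMRI and TMS".

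On data per person, the fMRI tasks paragraph has "Blocks will consist of seven images (28 seconds) for both rest and active conditions and six block cycles", and "participants will engage in two runs of each motor task". The two force-matching runs use different targets, 25% and 35% of maximum voluntary contraction (MVC). Section 6 (Participant selection) gives an example week with a single fMRI day, and no repeat scan within an assessment is described. The blood-sampling schedule refers to an Assessment 5. This fits scans at enrolment, after stretching, after each of the two interventions and at the end.

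Every participant is scanned twice before any training. The Aim 1 Research Design says: "After this waiting period, the participants again undergo behavioral, fMRI and TMS assessments".

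**The concern.** At group level, participants are the replicates, so session effects are judged against how much people differ in their change. Within one participant that yardstick is missing. Each assessment has one scan day, so session and scan day coincide, and the only replication left is cycles, runs, images or voxels inside the scan. The test then asks whether this person's response was the same on every scan day apart from within-scan noise. That is not the question whether training changed it. A shift in baseline state, head position, effort or scanner performance raises the chance of rejection with no training effect at all.

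At stake is how individual results would be read. The Aim 1 Research Design names fMRI change among the primary outcomes, and a participant with a significant session effect is easily taken for someone who responded to training.

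**Working it through.** The plan states no error rate for this test, so there is no figure to reproduce. The check gives the level of a one-person session test when training has no effect.

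**Inputs from the documents**
- Cycles per session, finger opposition: 2 runs × 6 = 12.
- Cycles per session, force matching: 6 per target, because each run has its own target.
- Sessions: s = 5 for the whole study, s = 2 for a before-after pair.

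**Assumptions**
- Nominal level 5%.
- Within-session error as the denominator. This is inferred: one scan day per assessment leaves no other source within one person's session test.
- k = between-session SD of the person's true response ÷ within-session standard error of the session estimate. The documents give no test-retest figure, so k is shown as a range.
- Normal errors and independent replicates.

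**Formula.** With m replicates in each of s sessions, the F ratio with no training effect is distributed as (1 + k²) × F(s−1, s(m−1)). The false-positive rate is P[F > Fcrit ÷ (1 + k²)].

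Example with m = 12 and k = 1:
- Five sessions: Fcrit(4, 55) = 2.54; 2.54 ÷ 2 = 1.27; rate 29.3%.
- Two sessions: Fcrit(1, 22) = 4.30; 4.30 ÷ 2 = 2.15; rate 15.7%.

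**False-positive rate (%), no training effect**

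| Replicates per session | Sessions | k=0 | 0.25 | 0.5 | 1 | 2 |
|---|---|---|---|---|---|---|
| 12 cycles (finger opposition) | 5 | 5.0 | 6.2 | 10.3 | 29.3 | 73.0 |
| 12 cycles (finger opposition) | 2 | 5.0 | 5.7 | 7.7 | 15.7 | 36.4 |
| 6 cycles (one force target) | 5 | 5.0 | 6.1 | 9.7 | 27.0 | 70.0 |
| 6 cycles (one force target) | 2 | 5.0 | 5.6 | 7.4 | 14.6 | 34.3 |
| 2 runs (finger opposition) | 5 | 5.0 | 5.6 | 7.5 | 16.2 | 47.1 |
| 2 runs (finger opposition) | 2 | 5.0 | 5.3 | 6.1 | 9.3 | 19.4 |

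A simulation of 40,000 participants per setting with 12 cycles agrees (k = 1: 29.2% and 15.7%). Treating cycle as a blocking factor changes little: 28.8% and 14.8% at k = 1.

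**Meaning of k.** With 12 cycles, k² = 12 × (scan-day variance ÷ per-cycle variance). So k = 0.5 is a scan-day variance of 0.25 ÷ 12 = 2.1% of the per-cycle variance, k = 1 is 8.3%, and k = 2 is 33%.

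**In people.** Among 40 participants, 2 would be flagged at nominal. With 12 cycles and five sessions the count is about 4 at k = 0.5 (40 × 0.103), 12 at k = 1 (40 × 0.293) and 29 at k = 2 (40 × 0.730).

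**Group level.** Simulating 40 people with scan-day variance 25% of per-cycle variance, the repeated measures ANOVA rejects in 5.0% (two sessions) and 5.3% (five sessions). It stays near its level.

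**Reference from the pre-training scans.** Let D be each person's change from enrolment to after stretching. For a later change x, use t = (x − mean D) ÷ [SD(D) × √(1 + 1/n)] on n−1 df. With n = 40, √1.025 = 1.012 and the critical value on 39 df is 2.02. In simulation the rate is 4.9% with no drift and 5.0% with a drift of 0.5 SD common to all changes. If mean D is not subtracted, the same drift gives about 8%.

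**The case against.** The strongest reply is that the plan never states a within-session error term. A repeated measures ANOVA across session normally has subjects as replicates, and assessing individuals and group can simply mean first- and second-level fMRI analysis. The paragraph opens with whether participants show a positive response at the outset, which is a single-session question, and intervention effects have their own group paragraph. This stands in part. The error term is inferred, and single-session activation maps are legitimate and should be kept. But the sentence directly follows the across-session test, so change within a person is the natural reading. On that reading, no choice of replicate unit removes the confounding of session with scan day.

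The second reply is that the size is unknown. That stands. A reader might infer that far more than 5% of participants will be falsely declared changed. The documents do not support this, because they give neither test-retest variance nor replicate unit, and the calculated range begins just above 5%. The plan also limits some sources of scan-day variation: image registration and intensity normalisation, practice outside and inside the scanner, paced presses, and force targets scaled to MVC with feedback.

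The third reply is that nothing planned uses the individual results. This also stands: the plan contains no responder count, and Section 7 tests Aim 2 with a group mixed model.

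**Conclusion.** The point holds as a defect of the individual-level clause only. As naturally read, the plan tests each participant's change between sessions with no between-session error term, and one person's session test has no usable source for one. The two pre-training scans give a single degree of freedom per person; they become useful only when pooled across people.

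The direction is clear: with within-session error and any scan-day variance above zero, the rate is above 5%. The size is conditional. For k from 0.25 to 2 it is about 6% to 73% over five sessions and 6% to 36% over two with 12 cycles. With runs as replicates it is about 6% to 47% and 5% to 19%.

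A reader might also infer that the intervention claim itself is undermined. It is not: the group-level tests hold their level, and no stated aim rests on individual significance. The point merits correction mainly because individual verdicts on a named primary outcome invite a responder reading.

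**What to change.** In the fMRI Analysis paragraph, restrict significance tests of session change to the group level, with subject as the random unit. State that individual-level analysis covers activation within a session. Do not use images, cycles, runs or voxels as replicates for a session effect.

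If individual change is to be reported, define it in advance. Take each person's change in right-M1 area under the response curve and subtract the mean change from enrolment to after stretching. Divide by the between-person SD of that pre-training change times √(1 + 1/n), and refer the result to t on n−1 df (39 for 40 completers). Report the counts descriptively by randomised group.

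State the assumptions with it. Test-retest variance is taken as similar across people. The reference interval is about three months and includes a stretching programme, so it may contain some real change. It is also shorter than the 26-week phase.

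The cost is a few sentences and no new scans, since both pre-training sessions are already planned. The downside is that fewer individuals will be labelled as changed.
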